#### Section 1 Regulatory Criterion for Approval: Risks are Minimized

Risks to subjects are minimized: (i) by using procedures that are consistent with sound research design and that do not unnecessarily expose subjects to risk, and (ii) whenever appropriate, by using procedures already being performed on the subjects for diagnostic or treatment purposes.

- Risks must be identified and classified as risks that would only be present if the subject participates in the research versus those risks that would happen as part of routine care or regardless of the subject's participation.
- > ONLY evaluate the **research** risks and consider how to minimize those risks:
  - o Is the question important scientifically/scholarly to answer?
  - Is the study designed so the question can be answered?
  - Can less risky procedures answer the question?
  - Can fewer procedures answer the question?
  - Are the procedures needed at all?
  - o Can additional procedures reduce risk?
  - Can different eligibility criteria reduce risk?
  - Are investigators and key personnel adequately qualified relative to the activities being performed and are the activities within each individual's scope of practice?
  - Are procedures that will answer the scientific question being done anyway? If so, can the data from these procedures be used to reduce the likelihood or magnitude of harm?

#### Study Design

A. Has this proposal undergone separate formal review to determine appropriateness of study design (i.e. formal Scientific Review Committee)?

**No** If NO, the IRB is responsible for determining that scientific design is appropriate

**Yes** If YES, describe the entity and outcome of the review (provide minutes or supporting documents in the submission package, if available): Click here to enter text.

#### B. Purpose of the study:

The purpose of the proposed clinical effectiveness pilot trial is to test the feasibility of a full-scale effectiveness trial comparing Peripherally Inserted Central Catheters (PICCs) to Long Peripheral Catheters (LPCs) in hospitalized pediatric patients. We aim to identify a population in which LPCs are safe and effective alternatives to PICCs for medium-term (5-14 days), non-central vascular access; data that will inform the design of a full-scale effectiveness study. Over time, use of LPCs should result in decreased inappropriate PICC utilization with a concomitant decrease in serious complications such as central line associated blood stream infection (CLABSI) and venous thromboembolism (VTE). We also aim to include patient/family feedback about their experience with these devices in the hospital.

#### C. Hypothesis/specific aims:

The aims of this pilot, randomized controlled trial are:

*Aim 1:* To assess the feasibility of a full-scale effectiveness trial comparing PICCs to LPCs in hospitalized pediatric patients in need of non-central, medium-term vascular access (5-14 days anticipated need). *Hypothesis:* Feasibility of a full-scale effectiveness trial will be established by demonstrating that > 70% of eligible patients agree to enrollment and randomization, > 80% of randomized patients receive the assigned intervention, > 80% of providers involved find the study acceptable, and < 5% of data are missing.

*Aim 2*: To identify a population in which a LPC is a safe and effective alternative to a PICC for vascular access in hospitalized pediatric patients age > 2 years, in need of non-central, medium-term access. *Hypothesis:* We hypothesize that LPCs are non-inferior to PICCs for delivery of peripherally compatible infusate needed for 5-14 days in hospitalized pediatric patients. We plan to determine the time-to-removal of the vascular access device, both secondary to completion of therapy and secondary to complications. Safety will be assessed by measuring complication rate (e.g., VTE, CLABSI, occlusion, dislodgement, phlebitis). Cross over rate will be closely monitored as well.

*Aim 3:* To engage patients and families as advisors in vascular access device selection. We will describe the patient and family experience with device placement and maintenance as well as perceived patient and parent insertion-related and sedation-related distress.

D. Background, significance, and rationale (including description of preliminary studies and any results):

Many hospitalized children require a vascular access device (VAD) for delivery of life saving interventions such as intravenous fluids and antibiotics.[1] With the broad range of VADs available, and their different profile of complications,[2] it is essential that clinicians have access to rigorous evidence to guide the selection of the most appropriate VAD. Appropriate VAD selection results in treatment efficiency and a decrease in catheter-related complications.[1] The problem is, even the most current and comprehensive guideline for VAD selection published in 2020, the Michigan Appropriateness Guide for Intravenous

Catheters in Pediatrics (mini-MAGIC), has gaps in recommendations and relies on expert consensus recommendations, acknowledging the lack of effectiveness and safety data for some VADs.[1,3] Peripherally Inserted Central Catheters (PICCs, see **Table 1**) are frequently used in hospitalized children for medium (5-14 days) and long-term access (> 14 days) and to administer solutions not compatible with peripheral infusion; however, concerns regarding potential inappropriate use (harm outweighing the benefits[4]) of PICCs were reported both in the adult and pediatric literature.[1,5,6] PICCs are central VADs associated with high rates of serious complications; Central Line Associated Blood Stream Infections (CLABSI) as high as 2-8.6% and Venous Thromboembolism (VTE) of 0-14% have been reported for PICCs.[2,7–11] At Children's Wisconsin, CLABSI was identified in 3.3% and VTE in 4.1% of PICCs during a 2012 to 2016 study period.[7] National collaboratives working to reduce hospital acquired conditions recognize CLABSI and VTE as 2 of the 9 *preventable* hospital-acquired conditions.[12]

One *critical* means of preventing PICC related complications and resultant patient harm is to prevent inappropriate placement of PICCs in cases when central venous access is not required (peripherally compatible infusate) and anticipated length of therapy is <14 days. Reducing inappropriate use of PICCs was shown to result in significant cost-savings over time, both in supplies, insertion and in cost reduction related to decrease in complications.[13,14] Attributable cost of CLABSI was reported to be \$55,646 per patient[15], and that of VTE was \$27,686.[16]

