#### E. Design and methods (including experimental design, technical details and laboratory methodology):

#### Study design:

Randomized clinical trial. We propose a parallel group, pragmatic randomized non-inferiority pilot trial design (*arm 1* and *arm 2*) (**Figure 1 below**) assessing the feasibility of a full-scale effectiveness trial comparing PICCs to LPCs for non-central, medium-term vascular access (5-14 days) in pediatrics.

Mixed methods (qualitative and quantitative data) will be used to determine patient/family experience.

**Setting and sample:** This single center pilot study will take place at Children's Wisconsin main hospital in Milwaukee. We plan to use convenience sampling, enrolling Monday through Friday 8-5pm during the one-year timeline.

Inclusion criteria: patients age 2 to 17 years admitted to Children's Wisconsin and requesting placement of a PICC () for: (1) anticipated length of intravenous treatment of 5-14 days, (2) planning peripherally compatible infusates [28] (3) VAD not needed at discharge.

Exclusion criteria: non-English-speaking family, active bacteremia or VTE at site where device would be placed, urgent need of vascular access (within 4 hours), another central venous catheter already in place, device needed for any intervention requiring central access such as medications that cannot be given peripherally OR central monitoring. To be included in the study, the treating attending physician will need to give approval for participation and randomization.

Inclusion/Exclusion criteria for guardian participation in the semi-structured interviews: > 18 years old, English speaking.

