#### / Study-wide (if applicable): N/A

**Describe what are these numbers are based on:** In a prior study, we showed that 139 PICCs over a one-year period could have been avoided at our local hospital as they (1) delivered peripherally-compatible infusates, (2) stayed in for < 14 days and (3) were removed prior to discharge. This is the population that we target for our study. For this pilot trial, we plan to enroll 35 patients in each randomized study group (35 participants in arm 1 and 35 participants in arm 2 of the study). The study is not powered to detect statistical significance, but rather to assess the feasibility of this study protocol for a larger full-scale effectiveness trial and provide baseline estimates for the sample size calculations. With a **sample size of 60 or more** patient subjects, we will be able to estimate a participation rate of 70% (eligible patients agree to enrollment and randomization) within a 95% confidence interval of +/- 12%.

The decision to include up to 70 adult guardians in the semi-structured interview portion was made to reach thematic saturation in qualitative analysis. Selection criteria for the interviews will be based on the number needed to meet qualitative saturation of data. All parents who enroll in the study will be asked to participate in the structured interview until qualitative thematic saturation is met. As such, selection criteria in effect will be based on chronology of participation in the study and number of interviews obtained from participants who agreed.

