#### D. Describe procedures to be employed in analyzing data (including a power analysis):

Quantitative. Study data will be collected using REDCap. Feasibility outcomes will be collected from (1) screening logs maintained by the study team (rate of enrollment, assigned intervention), (2) ease/difficulty of VAD placement (scale 0=worse to 10=best) to determine VAD acceptability, and (3) REDCap datasheet for assessing missed data. Patient demographics (age, gender, race/ethnicity), clinical factors (reason for admission, co-morbidities, reason for PICC/LPC request, therapy to be infused, requesting service, hospital floor), VAD data (VAD type and size placed, insertion site/vessel, sedation, number of attempts, additional VADs), effectiveness data (time-to-removal of VAD, prolonged NPO, number of lab draws from VAD, number of non-VAD blood draws) and complications requiring medical intervention will be collected using the EMR and daily (Monday-Friday) check-ins with the bedside nurse. Procedural pain with non-sedated VAD placement will be assessed in patients age > 5 years by the RC within 24 hours of insertion using the Faces Pain Score (FPS) or the 0-10 pain scale depending on the developmental age of the patient. Patient/parent anxiety and overall experience with VAD placement will be assessed on a 0-10 scale (0= lowest, 10=highest) and using the short State-trait anxiety inventory (STAI) that is validated in children 5 and older.

Descriptive statistics will be used to report feasibility outcomes and explore clinical factors (see above). Cross over rate will be calculated as the proportion of the number of subjects who crosses from the randomized arm/line to a different arm/line. The exact Clopper-Pearson 95% confidence interval will be generated. Time-to-device removal for all reasons will be compared using a t-test. Non-inferiority of LPCs to PICCs will be demonstrated if the 95% confidence interval of the mean difference lies above -1 (non-inferiority margin: 1 day). The remaining outcomes will be compared using Chi-square test or Fisher's exact for categorical variables and t-test or Mann-Whitney-Wilcoxon test for continuous variables. Where necessary for parametric assumptions, appropriate transformations will be employed. Non-parametric tests will be used where parametric assumptions are not satisfied. Logistic regression or general linear model will be performed to control the potential confounders.

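### The Aim 1 feasibility rule consists of four proportions and has no accrual criterion, so it can be met after a large recruitment shortfall

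*Combined protocol and SAP*

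**What the plan says.** Section 1 C, Aim 1, states when feasibility will be taken as established. The first of four conditions is agreement: "Feasibility of a full-scale effectiveness trial will be established by demonstrating that > 70% of eligible patients agree to enrollment and randomization". The other three are:

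- delivery: "> 80% of randomized patients receive the assigned intervention"
- acceptability: "> 80% of providers involved find the study acceptable"
- completeness: "< 5% of data are missing"

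The figures for scale and time stand elsewhere and are not tied to this rule:

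- Section 1 E (Setting and sample): "We plan to use convenience sampling, enrolling Monday through Friday 8-5pm during the one-year timeline".
- Section 3 A: "For this pilot trial, we plan to enroll 35 patients in each randomized study group", that is, 70 in total. The same section counts 139 potentially avoidable PICCs in one year as the source population.
- Sections 3 A and 6 D: a sample of 60 or more is said to estimate a 70% participation rate to within 12 percentage points.
- Section 6 D: feasibility data come from "screening logs maintained by the study team (rate of enrollment, assigned intervention") among other sources, and are summarized descriptively.

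The stopping rules in Section 6 C cover infection, thromboembolism, catheter failure and cross-over. None concerns accrual.

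**The concern.** The pilot exists to say whether a full-scale PICC versus LPC trial can be done. Whether enough children can be randomized in a reasonable time is central to that question. A rule made only of proportions does not depend on scale: 15 of 20 families agreeing counts for slightly more than 70 of 94 (75.0% against 74.5%). The plan has a target and a timeline, but the rule that delivers the main conclusion uses neither. A pilot that randomized a fifth or a third of its target could therefore report feasibility as established under its own prespecified criteria.

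**Working it through.** **1. The plan's own figure.** For p = 0.70 and n = 60, the 95% half-width is 1.96 × √(0.70 × 0.30 / 60) = 0.116, which rounds to the stated 12 points. The figure is sound. It describes the precision of a participation rate and is not a condition for declaring feasibility.

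**2. The benchmark the plan implies.** 70 randomized in 12 months is 70/12 = 5.8 per month. At exactly 70% agreement this needs 70/0.70 = 100 eligible families, or 100/139 = 72% of the yearly source population.

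**3. A direct counterexample.** Suppose 20 eligible families are approached in the year, 15 children are randomized (75%) and 13 of the 15 receive the assigned device (87%), with the provider and missing-data criteria met. All four thresholds are passed at 15/70 = 21% of target. The exact 95% interval for participation is then 51% to 91%.

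**4. How often this would happen.** Let N be the number approached, a the true agreement probability and r the true probability of receiving the assigned device. The probability that both criteria are met is

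P = Σ over x > 0.7N of Bin(x; N, a) × P[Bin(x, r) > 0.8x].

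The values of a and r are assumptions, since the documents give none. The provider and missing-data criteria are assumed met. N = 94 is the number that yields about 70 randomized at 75% agreement (70/0.75 = 93.3).

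| Approached | Randomized (expected) | a = 0.75, r = 0.90 | a = 0.80, r = 0.90 | a = 0.80, r = 0.95 |
|---|---|---|---|---|
| 20 | 15-16 | 0.55 | 0.72 | 0.79 |
| 32 | 24-26 | 0.68 | 0.85 | 0.91 |
| 94 | 70-75 | 0.88 | 0.99 | 0.99 |

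With 32 approached, about 35% of the target is randomized (24/70 = 34%, 26/70 = 37%), and the two criteria are still more likely met than not in every column.

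**5. Whether a shortfall is plausible.** The share of the 139 that can be reached in weekday office hours is not given, so it is varied here. If 5/7 are reachable, 139 × 5/7 × 0.70 ≈ 70 are randomized, with no margin. If half are reachable, 139 × 0.5 × 0.70 ≈ 49. Losses to attending, radiology or investigator veto (Section 3 D), or to absent parents (Section 4 C), would lower both. The 70% agreement ratio is the same in both cases, so it cannot register the difference.

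**6. What an accrual criterion would do.** Take at least 60 randomized in 12 months as an example, with Poisson counts. The probability of meeting it is below 0.001 at a true 24 per year, 0.05 at 48, 0.52 at 60 and 0.90 at 70.

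**The case against.** The strongest reply is that accrual is not ignored. Section 6 D names an enrollment rate as a feasibility outcome, Section 6 B schedules monthly meetings that cover enrollment and overall progress, and any report would show the number randomized beside the target of 70. The plan also calls itself unpowered and meant to supply baseline estimates, so a pass mark for every descriptive outcome might seem a matter of taste. Part of this stands: a reader might infer that planners of the full-scale trial would have no accrual information, and the documents do not support that. But the enrollment rate has no unit, target or threshold and may only mean the agreement proportion. Aim 1 goes beyond description, because it states when feasibility is established.

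Four other stronger readings also fail:

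- That the number randomized plays no part in the rule. It is the denominator of the device-receipt criterion; what is missing is an absolute count or target.
- That the rule hardly responds to poor recruitment. At 75% agreement and 90% receipt, the pass probability is 20 points lower with 32 approached than with 94 (0.68 against 0.88), and 33 points lower with 20 (0.55).
- That 60 is already the plan's accrual floor. It supports the precision of a participation rate, whose denominator is eligible patients; 60 eligible at 70% agreement would give 42 randomized.
- That slow accrual here implies a full-scale trial lasting decades. The documents do not fix that trial's sites, endpoint, variability or size, so no duration can be derived.

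**Conclusion.** The point holds in this form: the Aim 1 rule contains no absolute number randomized and no time element, and nothing elsewhere in the documents supplies one. Followed as written, it can declare feasibility after a large recruitment shortfall. With about 35% of the target randomized, the consent and device criteria are both met with probability 0.68 to 0.91, against 0.88 to 0.99 at the planned size. These figures rest on assumed agreement of 75-80%, assumed receipt of 90-95%, independent patients, and the other two criteria being met. The 20 and 32 approached are illustrations, not forecasts; the documents do not show that recruitment will fail. The structural gap and the counterexample of 15 randomized from 20 eligible need none of the assumed rates. This should be changed because it affects the pilot's main conclusion. It involves no error in a stated figure and no safety issue.

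**What to change.** In Aim 1, add a prespecified accrual criterion benchmarked to the plan's own 70 randomized in 12 months (about 5.8 per month). The sponsor should choose and justify the minimum acceptable number; 60 in 12 months is one option, with the probabilities shown in step 6. Require it jointly with the other four criteria.

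In Section 6 D, define the enrollment rate as randomizations per month from the screening log and report it with a Poisson 95% confidence interval.

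State the conclusion for a mixed result: if the four proportions are met but accrual is not, the design is acceptable but not feasible at this site's accrual without modification.

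The cost is a sentence or two in each section. The screening log should already supply the data, and no patients or procedures are added. The downside is that the verdict becomes somewhat harder to reach: with a floor of 60, a site truly accruing 60 per year would fail about half the time (1 − 0.52 = 0.48), and one accruing 70 per year about one time in ten.

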#### B. How do you plan to identify subjects for recruitment or records for inclusion in the study?

The entry point into the study will be the interventional radiology (IR) team which currently places PICCs. Each patient who has an order for PICC placement entered in the electronic medical record will be pre-screened by the IR provider using the Research Subject Eligibility Checklist posted in the IR workroom. Then the research team will verify IR has used this checklist, and will also screen each potentially eligible participant. Then the research team will screen each potentially eligible participation.

When a potential participant is identified, the attending physician of record (primary physician) will have to give his/her approval for study participation and confirm that the VAD needed satisfies the inclusion criteria (e.g. assure the VAD is not needed for central monitoring). A research subject eligibility checklist has been created for this purpose. The checklist will be posted in the Interventional Radiology workroom and used by Interventional Radiology for pre-screening prior to contacting the study team. The study team will verify the Interventional Radiologist has used this checklist. One the Interventional Radiologist confirms subject eligibility, the checklist will be reviewed with the attending physician, either in person or via phone between the attending physician and study team member. Physician name, date/time, and person completing form (if study team member via phone) will be documented on the form in addition to the determination. The completed checklist form will be stored in the subject's research file. See attached document in this package for the form. Attending physician and IR provider determinations will be entered by the study team into the screening log and the full checklist forms will be kept in the subject's research record.

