#### C. Eligibility Criteria (inclusion/exclusion criteria):

Inclusion criteria: patients age 2 to 17 years admitted to Children's Wisconsin with an order for placement of a PICC () for: (1) anticipated length of intravenous treatment of 5-14 days, (2) planning peripherally compatible infusates, (3) VAD not needed at discharge. Guardians of subjects enrolled in the randomization arm will be eligible for the structured interview study if > 18 year of age and English speaking. To be included in the study, the treating attending physician will need to give documented approval for participation and randomization using the research subject eligibility checklist, after Interventional Radiology and the PI have screened for eligibility. Exclusion criteria: non-English-speaking family, active bacteremia or venous thromboembolism at site where device would be placed, central VAD already in place, urgent need of vascular access (within 4 hours), device needed for any intervention requiring central access such as medications that cannot be given peripherally OR central monitoring

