## D. Who will be responsible for determining whether potential subjects satisfy eligibility criteria and how will they do so?

**Note:** if the analysis of health information is necessary to determine eligibility, a medically-qualified person must be involved in the determination.

A provider will place an order for a medically-indicated vascular access device to Interventional Radiology (IR). IR will pre-screen the patient for potential eligibility in the study. IR will page/volte the research team to screen and apply the eligibility criteria for study participation. The PI [name] will be responsible for making the final eligibility determination after approval by the primary attending physician of record and the interventional radiologist. If the attending physician, interventional radiologist, or PI determine the patient should not be approached, the patient will not be approached.

For the structured interviews in the randomized arms, the adult parent/guardian who signed the adult consent form to participate in the research study will be eligible.

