#### C. WHERE and HOW: Describe the physical location of the consent discussion and how it will be conducted:

The consent discussion will occur in the patient room with the guardian(s) and patient. After approval from the attending physician and PI, the research coordinator will coordinate with an identified care team member who will introduce the study team member to the family as a warm hand-off. The research coordinator will then approach the family in the patient room with the appropriate documents. If parents are not present in the room, the research coordinator will not attempt recruitment. Treating physicians will not be present in the room during the consent discussion in order to mitigate perceived power dynamics. The research coordinator will re-introduce herself and her role and present the study using a script. If the family indicates they would like to learn more, the research coordinator will review all consent information and assent with the family via the printed form and verbally. Time will be given to answer any questions. If the subjects choose to enroll, the research coordinator will obtain 1) signed documentation of parental permission for minor's participation in the study, 2) signed documentation of assent from the patient (if patient is capable) on the assent form document for subjects aged 7-13 or an assent line on the parental permission form for subjects aged 14-17, and 3) adult consent from the parent who will participate in the surveys and agree to the interview. The family will be provided copies of all consent materials.

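### The > 70% participation criterion does not define 'eligible': children whose physicians refuse randomisation can leave the denominator, and no Aim 1 criterion registers that loss or slow accrual

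*Combined protocol and SAP*

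**What the plan says.** Section 1, C makes feasibility depend on four thresholds. The first is that "> 70% of eligible patients agree to enrollment and randomization". The others are > 80% of randomised patients receiving the assigned device, > 80% of providers finding the study acceptable, and < 5% missing data.

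The attending's consent to randomisation appears among the eligibility criteria twice. The study design text (Section 1, E) says: "To be included in the study, the treating attending physician will need to give approval for participation and randomization". Section 3, C says: "the treating attending physician will need to give documented approval for participation and randomization using the research subject eligibility checklist". Section 3, D has the PI decide eligibility finally once the attending and the radiologist have approved, and adds: "If the attending physician, interventional radiologist, or PI determine the patient should not be approached, the patient will not be approached". No grounds are required.

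Later in the sequence, Section 4, C states: "If parents are not present in the room, the research coordinator will not attempt recruitment".

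On data, Section 3, B says: "Attending physician and IR provider determinations will be entered by the study team into the screening log". Section 6, D takes enrolment rate and assigned intervention from the screening logs as feasibility outcomes, reported descriptively, and uses a 0-10 rating of how easy placement was to judge acceptability.

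**The concern.** Every candidate already has a PICC order, so taking part means the treating team gives up its chosen device in half of cases. Whether physicians will allow that is a central feasibility question for this design. Yet on the most direct reading of Section 3, D, a child whose physician refuses is not eligible, is never asked, and cannot lower the participation rate.

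The other three criteria do not fill the gap. Device receipt and missing data concern children already in the trial. Provider acceptability sounds relevant, but the only measure named for it is ease of placement, which says nothing about willingness to randomise. Enrolment rate is collected but has no pass mark, so falling short of 70 children in the year would not in itself fail Aim 1.

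At stake is the pilot's main output. The stated rule could declare feasibility when physician refusals make recruitment unworkable. A pass/fail threshold with an open denominator can also be settled after the counts are known.

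**Working it through.** **The plan's own figure.** Section 3, A and Section 6, D state a precision of +/- 12% for 70% participation with 60 patients. The Wald half-width is 1.96 x sqrt(0.70 x 0.30 / 60) = 0.116, which rounds to 12 points. The figure reproduces, but it does not say which children are counted.

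**Inputs.**
- Consent threshold: 70% (Aim 1).
- Target: 70 randomised in one year (Section 1, E; Section 3, A).
- Pool: Section 3, A reports that "139 PICCs over a one-year period could have been avoided at our local hospital". This serves only as a rough pool.
- Approval share *a*, the proportion of clinically suitable orders passing all three approvals: not given. Assumed range 0.3 to 1.0.

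**Randomised share of suitable orders at exactly 70% consent** = *a* x 0.70. It falls below 50% when *a* < 0.50/0.70 = 71.4%.

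| Approval share *a* | Randomised share | Randomised per year if the pool is 139 |
|---|---|---|
| 1.0 | 70% | 97.3 |
| 0.9 | 63% | 87.6 |
| 0.8 | 56% | 77.8 |
| 0.7 | 49% | 68.1 |
| 0.6 | 42% | 58.4 |
| 0.5 | 35% | 48.6 |
| 0.3 | 21% | 29.2 |

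If the three approvals were independent with equal pass rates (an assumption), the break-even is 0.714^(1/3) = 89.4% each. At 80% each, 0.80^3 x 0.70 = 0.512 x 0.70 = 36%.

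**One data set under two denominators (assumed counts).** Take 139 suitable orders, 83 approved and 59 consenting.
- Eligible means after approval: 59/83 = 71.1%, criterion met.
- Eligible means clinical criteria only: 59/139 = 42.4% (Clopper-Pearson 95% CI 34.1% to 51.1%), criterion missed.

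**Parent-absent cases (assumed rates).** Suppose 70% are approved, a parent is present for 80% of those, and 75% of the families approached agree. If parent-absent children stay in the denominator, participation is 0.80 x 0.75 = 60%, a fail. If they are dropped, it is 75%, a pass. In both cases 0.70 x 0.80 x 0.75 = 42% of suitable orders are randomised.

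**Accrual.** 70/12 = 5.8 per month. At 70% consent, 70/0.70 = 100 children must be approached, which is 100/139 = 72% of the rough pool.

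**The case against.** The strongest reply is that the post-approval reading is not the only one. Section 3, B has the radiologist confirm eligibility before the checklist goes to the attending. Section 4, A screens for eligibility and then asks the attending's permission to approach. Both allow eligibility to be settled before approval. Section 3, C and D also differ on whether the attending's approval comes after or before the PI's determination. This stands: the defect is an undefined term, not a denominator the plan has expressly fixed after approval.

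A reader might infer that parent-absent children also drop out of the 70%. The documents do not support that. Absence of parents is not an eligibility criterion, and the rule operates after attending and PI approval. Read literally, those children are eligible, did not agree, and count against the criterion.

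A reader might also take 70/139 = 50.4% as the share of suitable orders the trial needs. But the 139 counts PICCs retrospectively, with no stated limits on age, language or minimum 5-day need. It is not a count of eligible patients.

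Some refusals will be correct application of the clinical criteria, since the attending must confirm that the device need fits them. Only refusals of otherwise suitable children are the problem. Finally, enrolment rate and two of the three determinations are recorded, so later planners would not be blind. That softens the consequence but does not alter the decision rule, which uses neither.

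**Conclusion.** The concern holds as a gap in the feasibility rule. On the most direct reading of Section 1, E and Section 3, C and D, physician refusals can leave the participation denominator. On any reading, none of the four criteria sets a standard for accrual.

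At exactly 70% consent, under half of suitable orders are randomised once approval is below 71.4%. If consent is higher, approval must be lower still for that to happen.

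A reader might conclude that only a minority of suitable orders will be randomised, or that the reported rate is bound to overstate recruitment. The plan gives no approval rate, so neither can be forecast. What can be said is that the criteria as written could not tell a workable trial from one blocked by physician refusal.

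**What to change.** 1. In Aim 1 and the analysis paragraph of Section 6, D, state whether eligibility is judged before or after physician approval, and how parent-absent cases count. Reconcile the order of approvals between Section 3, C and D.
2. Keep family agreement among approved patients as one figure. Add two prespecified feasibility outcomes: the physician approval rate, and the randomised share of all recruiting-hours PICC orders that meet the clinical criteria. Give Clopper-Pearson 95% intervals, which the plan already uses for cross-over, and a threshold that the sponsor sets before analysis. Carrying 70% over automatically would be a different and much harder test: consent would have to exceed 0.70/0.9 = 77.8% at 90% approval and 0.70/0.8 = 87.5% at 80%, and the test could not be met at 70% approval or below.
3. Add an accrual criterion against the planned 70 in one year, or 5.8 per month.

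**Cost.** Mostly wording. The screening log is stated to hold attending and radiologist determinations. PI refusals, parent absence and the reason for each refusal (clinical ineligibility or unwillingness to randomise) must be added. The feasibility result may look less favourable.
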